10.2.1 List of Tables

- The NAb positive response rates by cell type, isolate, visit and group.
- Lists of the positive responders and the titer for those participants.
- Summary statistics for NAb titers among the positive responders.
- The comparisons of response rates between groups by cell type, isolate, and visit.
- The comparisons of titers between groups by cell type, isolate, and visit.
- The comparison of AUC-MB between groups by visit

10.2.2 List of Figures

- Boxplots of neutralizing antibody titers by cell type, isolate, visit, and group.
- Spaghetti plots of neutralizing antibody titer over time by cell type, isolate, and group
- Reverse CDFs of neutralizing antibody titers by cell type, visit and group
- Magnitude-breadth (MB) plots of titer and breadth for a panel of viruses by cell type, visit, and group

10.3 Antibody-Dependent Cell-Mediated Cytotoxicity (ADCC)

The GranToxiLux ADCC (GTL-ADCC) assay will be used to test reactivity against HIV-env protein coated cells (% Granzyme readout). Cells coated with either gp120 protein A, gp120 protein B, gp120 protein AE, or Clade C TV1 gp120 individually will be tested in a 96 well plate for the Grantoxilux (GTL assay). Participant sera in addition to control sera will be incubated with these HIV proteins and ADCC detected through the use of a Granzyme B substrate (GTL).

Cells infected with HIV-1 IMC TV1, WITO and CM235, individually, will be tested in a 96 well plate for the Luciferase ADCC assay. Participants sera in addition to controls were incubated with the IMC-infected cells and ADCC detected through the use of Vivirene luminescence.

The following evaluation criteria will be employed for this assay:

- i) GTL: The data from the assay is quantitative. The frequency of positive responses (% responders) peak ADCC, and area under the curve (AUC) will be tabulated to assess differences in ADCC response between the treatment groups.
- ii) Luciferase: The data from the assay is semiquantitative. The frequency of positive responses (% responders) peak of specific killing and AUC will be tabulated and compared between the treatment groups.

Positivity criteria are as follows:

- i) GTL: peak % response $\geq 8\%$

- ii) Luciferase: peak % response $\geq 10\%$, after background subtraction of baseline response and positivity at one of the first two dilutions.

The sera samples at v12 (day 0) and v22 (day 238) from the 48 participants in Part B will be assayed for ADCC responses. Based on the responses at v22, assays may be performed on these participants samples at v17 (day 98), v19 (day 182), and v24 (day 425).

Positive response rates will be compared between treatment groups within each time point using Barnard exact test. Peak of ADCC and AUC ADCC will be compared between treatment groups within each time point using Wilcoxon rank sum test. Positive response rates, peak ADCC, and AUC ADCC between time points within treatment group will be also compared using McNemar's tests and Wilcoxon signed rank test, respectively, if neutralizations will be measured at multiple time points.

Magnitude-Breadth (MB) of peak ADCC and of AUC ADCC will be calculated and displayed for each of two ADCC assays. AUC-MB of peak and AUC ADCC will be compared between the treatment groups within each time point using Wilcoxon rank sum test and between time points within each treatment group using Wilcoxon signed rank test.

In addition, we will evaluate the correlation of AUC-MB of peak ADCC at each time point measured by the Luciferase and the GTL assays. We will also evaluate the correlation of AUC-MB of AUC ADCC at each time point measured by the Luciferase and the GTL assays.

10.3.1 List of Tables

- Response rate of peak net percent Granzyme B activity by treatment group, protein, and visit
- Summary statistics (i.e., min, mean, median, max) of peak net percent Granzyme B activity among all participants by treatment group, protein, and visit
- Summary statistics (i.e., min, mean, median, max) of peak net percent Granzyme B activity among positive responders by treatment group, protein, and visit
- Summary statistics (i.e., min, mean, median, max) of AUC peak net percent Granzyme B activity among all participants by treatment group, protein, and visit
- Summary statistics (i.e., min, mean, median, max) of AUC peak net percent Granzyme B activity among positive responders by treatment group, protein, and visit
- Listing of positive peak net percent Granzyme B
- Response rate comparison of peak net percent Granzyme B activity at v22 (possibly v17, v19, v24) between T2 and T3 by protein
- Response magnitude comparison of peak net percent Granzyme B activity at v22 (possibly v17, v19, v24) between T2 and T3 by protein
- Comparison of AUC peak net percent Granzyme B activity at v22 (possibly v17, v19, v24) between T2 and T3 by protein
- Response rate of peak of specific killing by treatment group, protein, and visit
- Summary statistics (i.e., min, mean, median, max) of peak of specific killing among all participants by treatment group, protein, and visit
- Summary statistics (i.e., min, mean, median, max) of peak of specific killing among positive responders by treatment group, protein, and visit

- Summary statistics (i.e., min, mean, median, max) of AUC peak of specific killing among all participants by treatment group, protein, and visit
- Summary statistics (i.e., min, mean, median, max) of AUC peak of specific killing among positive responders by treatment group, protein, and visit
- Listing of positive peak of specific killing
- Response rate comparison of peak of specific killing at v22 (possibly v17, v19, v24) between T2 and T3 by protein
- Response magnitude comparison of peak of specific killing at v22 (possibly v17, v19, v24) between T2 and T3 by protein
- Comparison of AUC of specific killing at v22 (possibly v17, v19, v24) between T2 and T3 by protein
- Comparison of AUC-MB of peak ADCC at v22 (possibly v17, v19, v24) between T2 and T3
- Comparison of AUC-MB of AUC ADCC at v22 (possibly v17, v19, v24) between T2 and T3
-

10.3.2 List of Graphs

- Boxplots of Peak Percent Granzyme B Activity by protein and treatment arm
- Boxplots of AUC Percent Granzyme B Activity among positive responders according to the peak activity criterion by protein and treatment group
- Boxplots of Peak of specific killing by protein and treatment group
- Boxplots of AUC specific killing among positive responders according to the peak activity criterion by protein and treatment group
- MB plot of Peak ADCC by treatment group, visit, and assay type
- MB plot of AUC ADCC by treatment group, visit, and assay type
- Scatterplot and regression line of AUC-MB of peak ADCC measured by the Luciferase vs AUC-MB of peak ADCC measured by the GTL for each time point (excluding placebos and color-coding for the treatment group T2 and T3)
- Scatterplot and regression line of AUC-MB of AUC ADCC measured by the Luciferase vs AUC-MB of AUC ADCC measured by the GTL (excluding placebos and color-coding for the treatment group T2 and T3)

10.4 Intracellular Cytokine Staining (ICS)

Immunogenicity will be assessed by ICS using PTE_G Peptide Pools (Env-1-PTEG-SEQ, Env-2-PTEG-SEQ, Gag-1-PTEG-SEQ, and Gag-2-PTEG-SEQ) covering Gag and Env. The 17-color ICS staining panel [CD3 BUV737, CD4 BUV395, CD8 BV650, CD14 BV510, CD56 BV570, CXCR5 PE-Dazzle594, PD-1 (CD279) BV605, ICOS (CD278) BV711, CD45RA APC H7, CCR7 BV786, IFN- γ V450, TNF- α FITC, IL-2 PE, IL-4 PerCP-Cy5.5, IL-17a PE-Cy7, CD154 APC, Granzyme B Alx700] will be used. ICS will be assayed on the samples from all 48 Part B

participants at primary immunogenicity time point (visit 22, two weeks post the 5th vaccination). ICS may also be assayed at secondary immunogenicity time points (e.g. 2 weeks post the 3rd vaccination and 6 months post the last vaccination). Response of CD4+/CD8+ T cells measured by ICS for IFN- γ and/or IL-2 to any HIV PTE peptide pools (Env-1-PTEG-SEQ, Env-2-PTEG-SEQ, Gag-1-PTEG-SEQ, and Gag-2-PTEG-SEQ) covering all genes or individual genes (especially Env and Gag) are primary immunogenicity endpoints. To be specific, the response of CD4+/CD8+ T cells to Env is defined as a sum response to the peptides, Env-1-PTEG-SEQ and Env-2-PTEG-SEQ, the response to Gag is defined as a sum response to Gag-1-PTEG-SEQ and Gag-2-PTEG-SEQ; and the response to any protein is defined as the sum of the response to Env and the response to Gag. Fisher exact test criteria will be used for positivity calls before assay on all samples are complete.

The COMPASS (Combinatorial Polyfunctionality analysis of Antigen-Specific T-cell Subsets) statistical framework (Lin, et al. 2015) may also be used to perform joint modelling of multiple T-cell subsets of different cytokine combinations. The functionality score (FS) and the polyfunctionality score (PFS) may be used to summarize the multi-parameter ICS responses.

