A first-generation version of the DNA prime-protein boost regimen developed by the University of Massachusetts Medical School (UMMS) team generated significant Env-specific antibodies, low titer but cross-clade neutralizing antibodies, and cell-mediated immune (CMI) responses (both CD4 and CD8 T cells) in participants in the DP6-001 study (5, 26) (see Section 4.8.1). In HVTN 124, CD4+ and CD8+ T cell responses will also be analyzed.

To improve upon the immunogenicity and safety profile observed in the DP6-001 study, several modifications have been made to the vaccine formulations for HVTN 124. One change is to further enhance the immunogenicity of Env antigens by carefully selecting optimal gene inserts from four different HIV-1 subtypes. Also, the adjuvant to be administered with the protein vaccine, GLA-SE, differs from the QS-21 adjuvant that was used in the DP6-001 study. QS-21 has been associated with an increased risk of adverse events of the skin in other clinical studies (27). To further minimize risk, this study will enroll participants in stages, to monitor for any adverse reactions (Section 11.3).

In summary, the primary goal of this study is to evaluate the safety and immunogenicity of the polyvalent DNA - protein HIV-1 vaccine regimen with newly optimized inserts for Envs from subtypes A, B, C, and A/E, and for subtype C Gag (DNA only), building on results from the DP6-001 study which

demonstrated balanced humoral and cellular immune responses, including cross-clade neutralization of pseudoviruses expressing Env antigens.

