4.3 Recombinant gp120 (A,B,C,A/E) protein with GLA-SE adjuvant

4.3.1 Recombinant gp120 protein vaccine

The recombinant gp120 (A,B,C,A/E) protein vaccine contains equal amounts of 4 gp120 proteins matching the Env genes used in the DNA vaccine, produced in stable CHO cell lines by Waisman Biomanufacturing (Madison, WI) under GMP compliant conditions. The gp120 proteins are highly glycosylated and consist of 5 relatively conserved domains (C1-C5) interspersed with 5 hypervariable domains (V1-V5).

Each of the 4 gp120 proteins will be produced and vialled individually.

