4.4.1 Safety

In order to carefully evaluate the safety of each component of the vaccine strategy, HVTN 124 will be conducted in two parts. Part A will evaluate the safety and immunogenicity of the protein vaccine with adjuvant, independent of the DNA prime. In Part B, the prime-boost regimen of 3 DNA primes (months 0, 1, 3) followed by 2 protein/adjuvant boosts (months 6, 8) will be compared to a study arm consisting of the DNA and protein/adjuvant vaccines co-administered at the same timepoints (months 0, 1, 3, 6, 8). Therefore Part B will evaluate the safety of the DNA prime individually or in combination regimens.

The protocol will enroll each part of the study in stages, with frequent safety reviews (see Section 11.3). The group sizes in Part B will allow for reasonable precision in the characterizations of the safety endpoints, as well as reasonable power for comparisons between the groups with respect to immunogenicity endpoints, particularly with assays that might have less frequent responses, such as Tier 2 neutralizing antibodies (see Sections 6.1.1 and 6.1.2).

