10.3 Primary immunogenicity timepoint

The primary immunogenicity timepoints in this study occur 2 weeks after the last vaccination for Parts A and B. Endpoint assays for humoral and cellular responses are performed on specimens collected from participants at the primary immunogenicity timepoints and may be performed on samples collected at baseline. Depending on the initial results, assays for humoral and cellular responses may be performed on samples collected from participants at other timepoints; the schedule is shown in [Appendix H](#) and [Appendix I](#).

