3.2 Secondary Objectives and Endpoints

Secondary objective 1:

- To evaluate the serum IgG binding antibody responses to Env proteins elicited by each vaccination regimen

Secondary endpoint 1:

- Magnitude and breadth of serum HIV-1 Env-specific IgG responses assessed by Binding Antibody Multiplex Assay two weeks after the last vaccination

Secondary objective 2:

- To evaluate the serum neutralizing antibody responses elicited by each vaccination regimen in Part B

Secondary endpoint 2:

- Serum neutralizing antibody responses against Tier 1A, Tier 1B, and selected Tier 2 viruses, assessed by TZM-bl assay, two weeks after the last vaccination in Part B

Secondary objective 3:

- To evaluate each vaccination regimen with specific antibody assays to measure correlates of risk identified in the RV144 trial

Secondary endpoint 3:

- Breadth of gp70-V1V2 IgG and gp120 IgA, assessed by Binding Antibody Multiplex Assay, and ADCC activities against HIV-1 subtypes A, B, C and A/E two weeks after the last vaccination in Part B

Secondary objective 4:

- To evaluate HIV-specific T-cell responses elicited by each vaccination regimen

Secondary endpoint 4:

- Frequency, magnitudes and quality of HIV-1 specific CD4+ and CD8+ T-cell responses as measured by ICS two weeks after the last vaccination

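### SAP 10.4 assigns ICS samples from Part B only, although secondary endpoint 4 and the protocol's assay schedule also cover the protein/GLA-SE-only arm (T1) in Part A

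*SAP*

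**What the plan says.** SAP 3.2 sets secondary objective 4 as "To evaluate HIV-specific T-cell responses elicited by each vaccination regimen". Its endpoint is "Frequency, magnitudes and quality of HIV-1 specific CD4+ and CD8+ T-cell responses as measured by ICS two weeks after the last vaccination". Neither is limited to Part B, whereas endpoints 2 and 3 in the same section are. Protocol 5.2 words objective and endpoint 4 the same way.

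SAP 10.4 then sets the sample rule: "ICS will be assayed on the samples from all 48 Part B" participants, at visit 22, two weeks after the fifth vaccination. It allows assays at secondary timepoints, giving as examples two weeks after the third vaccination and six months after the last. No Part A visit is named.

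The protocol includes Part A. Section 10.3 says: "The primary immunogenicity timepoints in this study occur 2 weeks after the last vaccination for Parts A and B", and that humoral and cellular endpoint assays are performed at those timepoints. The heading of Section 10.4.1 assigns flow cytometry to both parts. Appendix H shows an ICS draw of 42.5 mL at Part A visit 5, and its footnote 6 places the immunogenicity assays at Month 2.5.

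**The concern.** T1 is the only arm that receives the protein vaccine without DNA. Protocol 4.4.1 gives that as a purpose of Part A: "Part A will evaluate the safety and immunogenicity of the protein vaccine with adjuvant, independent of the DNA prime". If the laboratory and the statisticians take their ICS sample list from SAP 10.4, T1 is left out of an endpoint promised for every regimen, and blood is drawn in Part A for an assay that the SAP does not assign.

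Timing adds some weight. Part A runs before Part B (protocol 6.1) and is unblinded independently of it (SAP 7). Its ICS sample set is therefore best fixed in the SAP before any Part A T-cell data are seen.

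**Working it through.** **1. Reproduce the SAP's count.** From the schema, Part B = 2 × (21 + 3) = 48 and Part A = 10 + 2 = 12, for a total of 60. The SAP's figure of 48 is therefore exactly Part B.

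**2. Can the named visit include Part A?** No. Visit 22 follows a fifth vaccination, and Part A has two vaccinations (Months 0 and 2). The optional timepoints are secondary ones, and neither example is Part A's primary timepoint, Month 2.5.

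**3. Is the Appendix H entry real or a table-reading artefact?** Adding the visit 5 column gives 10 (HIV diagnostics) + 5 (CBC) + 5 (chemistry) + 42.5 (ICS) + 8.5 (binding antibody) + 76.5 (PBMC) + 17 (serum) = 164.5 mL. This equals the printed visit total, so the ICS draw belongs in that column.

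**4. Compare the four assays.**

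| Assay | Protocol scope | SAP sample set | Agree? |
|---|---|---|---|
| BAMA | Parts A and B (10.5.1) | Part A visits 2 and 5, plus Part B (10.1) | yes |
| Neutralization | Part B (10.5.2) | 48 in Part B (10.2) | yes |
| ADCC | Part B (10.5.3) | 48 in Part B (10.3) | yes |
| ICS | Parts A and B (10.4.1) | 48 in Part B (10.4) | no |

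Only ICS departs from the protocol, and SAP 10.1 shows how a Part A visit is listed when it is intended.

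**5. Size of the gap.** Vaccinees with no ICS sample assigned: 10/52 = 19.2%. Participants: 12/60 = 20%.

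**6. What T1 could show if added.** The score interval of SAP 8.4.1, with z = 1.96 and p = x/n, is

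(p + z²/2n ± z·√[p(1−p)/n + z²/4n²]) / (1 + z²/n).

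As a check, it reproduces protocol Table 6-2 (0/10 [0, 27.8], 1/10 [1.8, 40.4], 2/10 [5.7, 51.0]) and Table 6-3 (9/18 [29, 71]). Then:

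- n = 10: 0/10 [0, 27.8]%, 5/10 [23.7, 76.3]%, 10/10 [72.2, 100]%.
- n = 9, after the 10% early missing rate in protocol 6.1 (10 × 0.9 = 9): 0/9 [0, 29.9]%, 9/9 [70.1, 100]%.
- P_A, n = 2: 0/2 [0, 65.8]%. This is a listing and not a usable background rate.

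The chance of seeing at least one responder among 10 reaches 90% at a true rate of 1 − 0.1^(1/10) = 20.6%, the figure that protocol 6.1.1 gives for events in this arm.

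**7. Which readout applies to T1?** The protein vaccine "contains equal amounts of 4 gp120 proteins matching the Env genes used in the DNA vaccine", and protocol 4.1 describes the inserts as including those "and for subtype C Gag (DNA only"). T1 therefore receives Env and no Gag. SAP 10.4 defines an any-protein readout: "the response to any protein is defined as the sum of the response to Env and the response to Gag". SAP 10.4.1 also reports Env and Gag separately, so the Env row already gives the result that matters for T1.

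**The case against.** The strongest reply is that the SAP does not exclude Part A. SAP 10.4 never says that only Part B is assayed. SAP 8.4.1 tabulates each assay by treatment arm at every timepoint assessed, and the ICS tables and graphs are set out by visit and treatment arm. If the protocol-required assay is run, those outputs can take T1. SAP 1 also expects later revisions on immunogenicity. All of this stands. A reader might infer from SAP 10.4 that T1 will have no T-cell result, but the documents do not support that. They show that no Part A sample is assigned in the SAP, while the protocol still draws and plans it.

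A reader might also infer that the Part B readouts cannot serve T1 because they include Gag. That does not follow either, since Env is tabulated separately and the Gag and any-protein rows do no harm if read for what they are.

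The protocol is also not uniform on Part A's role. Section 6.1 describes Part A as assessing safety and Part B as evaluating safety and immunogenicity, and the immunogenicity sizing in 6.1.2 concerns Part B only. This is a fair reason to ask the authors to confirm intent. It does not outweigh Sections 4.4.1, 10.3, 10.4.1 and Appendix H, which all include Part A immunogenicity, nor an endpoint with no Part B limit beside two that have one.

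Finally, no planned test changes and n = 10 is small. Both are true. They limit the consequence but do not remove the mismatch.

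**Conclusion.** The mismatch is real and within the SAP itself: endpoint 4 covers each regimen, while the ICS sample rule covers Part B alone. The protocol agrees with the endpoint. Followed literally, SAP 10.4 leaves T1 out of secondary endpoint 4 (10 of 52 vaccinees). An unintended omission is the likeliest reading, because ICS is the only one of four assays out of line, but the documents do not state the cause.

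The consequence is limited to description. SAP 10.4.1 plans only T2 versus T3 comparisons, and these keep their data and precision. The conclusion needs no assumption beyond reading SAP 10.4 as the list of samples to be assayed. The intervals assume 10 evaluable T1 participants, or 9 with the protocol's 10% missing rate.

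**What to change.** In SAP 10.4, add the visit 5 (Month 2.5, two weeks after the second vaccination) ICS samples from all 12 Part A participants. State that T1 and P_A will be reported descriptively in the existing ICS tables and graphs, with the score 95% intervals of SAP 8.4.1. State also that T1 is read mainly on the Env row because it receives no Gag. Add no tests against T2 or T3. Make the change before Part A ICS data are reviewed.

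The cost is 12 assays whose blood draw the protocol already schedules, plus a few sentences at a revision that the SAP already expects. No sample size or planned comparison changes.

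If the authors did intend ICS for Part B only, they should limit endpoint 4 to Part B in both documents, give the reason, and remove the Part A ICS draw. That is the dearer route, since it touches protocol 5.2, 10.3, 10.4.1 and Appendix H as well as the SAP.

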10.4.1 List of Tables

- Response rate table by T-cell subset, HIV protein (Any, Env, Gag), visit, treatment arm for cells expressing either IL-2 and/or IFN- γ using Fisher's exact test criteria.
- Listing of positive responders for cells expressing either IL-2 and/or IFN- γ based on the criteria used for the response rate table(s).
- Summary statistics (i.e., min, mean, median, max) among responders for T-cell subset, HIV protein, visit, and treatment arm.
- Response rate comparison between T2 and T3 by T-cell subset, HIV protein, and visit using Barnard exact test.
- Response magnitude comparison between T2 and T3 by T-cell subset, HIV protein, and visit using Wilcoxon rank sum test.
- Summary statistics (i.e., min, mean, median, max) of FS and PFS for T-cell subset, HIV protein, visit, and treatment arm.
- FS and PFS comparison between T2 and T3 by T-cell subset, HIV protein and visit using Wilcoxon rank sum test.

10.4.2 List of Graphs

- Bar-chart of response rate by T-cell subset, HIV protein, visit, and treatment arm using Fisher exact test.
- Boxplots of background-adjusted IFN- γ and/or IL-2 response magnitude by T-cell subset, HIV protein, visit, and treatment arm using Fisher exact test
- Boxplots of background-adjusted marginal cytokine response magnitude by T-cell subset, HIV protein, visit, and treatment arm using Fisher exact test
- Boxplots of FS/PFS by T-cell subset, HIV protein, visit, and treatment arm.

